### 6.1.4 History of Rheumatoid Arthritis

The study participants' history of RA will be summarized on the SS and listed. The following RA history variables will be included:

- Presence of extra-articular features (ever had and present at Screening)
- Duration of RA (first persistent symptoms). Duration of RA should be calculated as the difference between screening date and first persistent symptoms. If the date of diagnosis is partial, it should be imputed to the most recent feasible date (ie, last day of the month if only day is missing, or the last day of the year if day and month are missing). Sometimes Baseline date is used instead of Screening date.
- Duration of RA (since date of diagnosis). Duration of RA should be calculated as the difference between screening date and date of diagnosis. If the date of diagnosis is partial, it should be imputed to the most recent feasible date (ie, last day of the month if only day is missing, or the last day of the year if day and month are missing). Sometimes Baseline date is used instead of Screening date.
- Duration category of RA since first diagnosis (typically < 2 years and ≥ 2 years, but other cutpoints may be used depending on the study).
- Duration of RA (years) will be calculated as:
  - Duration of RA (first persistent symptoms) = (screening date - first persistent symptoms) / 365.25
  - Duration of RA (since date of diagnosis) = (screening date - date of diagnosis) / 365.25.

History of rheumatoid arthritis will be listed for the SS for all study participants including date of first persistent symptoms of RA, date of first diagnosis, history or current of extra-articular features (keratoconjunctivitis sicca (yes/no), rheumatoid nodules(yes/no), scleritis(yes/no), neuropathy(yes/no), vasculitis(yes/no), pulmonary fibrosis(yes/no), other ).

## **6.1.5 Prior/concomitant medications**

### **6.1.5.1 Prior medication definition**

Prior medications include any medications that started prior to the start date of study medication. If a participant takes a medication before the date of administration of IMP, this medication will be classified as 'prior medication'. With this definition, any medication recorded that has been taken for at least 1 day before the date of administration of IMP will be considered as prior. This includes medications that started prior to dosing and continued after.

### **6.1.5.2 Concomitant medication definition**

Concomitant medications are medications taken at least one day in common with the study medication dosing period. For Cimzia, the dosing period is typically from the date of first dose up to (but not including) 14 days post last dose. Thus, a concomitant medication is any medication whose start date is prior to the date of last study medication administration + 14 days, and whose stop date is either missing, or on or after the date of first study medication administration.

From the definitions above, any medication that started prior to dosing and continued after dosing will be classified as both prior and concomitant.

Any medications with missing dates and/or times will be handled as described in Section 6.1.6.2 in order to classify them as prior or concomitant.

Prior and concomitant medications will be listed and summarized, separately, for the SS for all study participants by WHODD version Sep/2020 B3 update Anatomical Main Group [Level 1], Pharmacological Subgroup [Level 3], preferred term (PT) and reported term (listing only).

Separate tabulations will be presented for the following:

- Prior medications
- Concomitant medications

All medications will be listed including glossary and will include coding information, reported term, dose per intake and unit, frequency, formulation, route of administration, indication, category (prior/concomitant) and start and end date (or ongoing, if applicable).

## **6.1.6 Data derivation rules**

### **6.1.6.1 Handling of repeated and unscheduled measurements**

All repeated and unscheduled measurements will be presented in the listings. Repeated and unscheduled measurements will not be used for statistical analysis or summary tables, unless the repeated measurement was performed due to unreliable values/technical reasons, or the repeated measurement occurred prior to Investigational Medicinal Product (IMP) administration and is defined as the 'baseline'. The following general rules will apply to all repeated and unscheduled measurements:

- For repeated measurements obtained prior to the first dose of IMP the latest reliable value (which may be scheduled or unscheduled) will be used in the calculation of descriptive statistics
- For repeated measurements obtained at the designated Baseline visit, the latest reliable value (which may be scheduled or unscheduled) will be defined as the Baseline. Repeated measurements designated Baseline will be used in descriptive statistics rather than the planned measurement they replace
- For repeated measurements obtained at any time point after the first dose of IMP, the first reliable value of any repeated measurements will be used in the calculation of changes from Baseline and for the descriptive statistics.

#### 6.1.6.2 Handling of Dates and times

Partial dates may be imputed for the following reasons:

- Classification of adverse events (AEs) as treatment-emergent AEs
- Classification of medications as prior or concomitant
- Durations of AEs.

Imputed dates will not be shown in the listings; all dates will be displayed as reported in the database.

The following rules will be applied for partial start dates/times:

If time is not collected for a certain domain, time will not be imputed for that domain.

- If only start month and year are specified and not the same as month and year of dosing then use the 1st of the month, or the date of screening if this is later (if the latter imputation results in an end date that is earlier than the start date, then use the 1st of the month). If time is missing this will be imputed as 00:00 h;
- If only the month and year are specified and the month and year of dosing is the same as the month and year of the start date, then use the date of dosing. If this results in an imputed start date that is after the specified end date, then use the 1st of the start month, or the date of screening if this is later (if the latter imputation results in an end date that is earlier than the start date, then use the 1st of the month). If the imputed date is the date of dosing then time will be imputed as the start time of the sc injection (ie, event will be regarded as treatment-emergent);
- If only the year is specified, and the year of dosing is not the same as the year of the start date then use January 01 of the year of the start date. If time is missing this will be imputed as 00:00 h;
- If only the year is specified, and the year of dosing is the same as the year of the start date, then use the date of dosing. If this results in an imputed start date that is after the specified end date, then use January 01 of the year of the start date, or the date of screening if this is later (if the latter imputation results in an end date that is earlier than the start date, then use January 01). If the imputed date is the date of dosing then time will be imputed as the start time of the sc injection (ie, event will be regarded as treatment-emergent);
- If the start date is completely unknown, then use the date of dosing. If this results in an imputed start date that is after the specified end date, then use January 01 of the year of the end date, or the date of screening if this is later (if the latter imputation results in an end date that is earlier than the start date, then use January 01). If the imputed date is the date of dosing then time will

be imputed as the start time of the sc injection (ie, event will be regarded as treatment-emergent).

Any medication with a start date on the dosing date and time unknown, will be assumed to be concomitant.

The following rules will be applied for partial stop dates:

- If only the month and year are specified, then use the last day of the month;
- If only the year is specified, then use December 31 of the known year;
- If the stop date is completely unknown, do not impute the stop date

Missing or partially missing date and/or times will be imputed as described in [Table 6-1](#) for the calculation of duration of each AE. Adverse event duration is computed in and reported in day and time format: xx d hh:mm.

**Table 6-1: Calculation rules for duration**

Data availability	Onset date/time	Outcome date/time	Calculation rules
Complete data	D1/T1	D2/T2	Duration = [(D2 - D1)*24 + (T2 - T1)]/24 d
End time missing	D1/T1	D2/--	End time is substituted by time 23:59h (=23.98 in decimal format) Duration = <[(D2 - D1)*24 + (23.98 - T1)]/24 d
Start time missing	D1/--	D2/T2	Onset time is substituted by time 00:00h. Note: if onset date is on the same date of first study administration, then the time point of first study administration will be used for missing onset time. Duration ≤ [(D2 - D1)*24 + T2] / 24 d
Start and end time missing	D1/--	D2/--	Duration = <D2 - D1 + 1
Start day and time missing	--/--	D2/T2	Duration = <[(D2 - D0)*24 + (T2 - T0)]/24 d For a participant in the SS, D0 and T0 are the date and time of dosing and for screen failures, D0 is the date of the screening visit and T0 = 00:00h
End day and time missing	D1/T1	--/--	For ongoing AE: Duration = >Discharge day - D1 d OR For resolved AE: Duration = <Discharge day - D1 d OR Where discharge refers to the date of the end of study visit for completed study participants or the date of discontinuation for study participants that were withdrawn. For any AEs with known start date/time after the date of discontinuation, the date of last contact will be used as the discharge day.

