#### **5.4.1.2.3 Treatment-emergent AEs leading to withdrawal**

Similarly, the analysis for treatment emergent AEs leading to withdrawal from the time of the first CZP dose through the SFU Visit will be included as follows:

- Incidence of treatment emergent AEs leading to withdrawal
- Incidence of treatment emergent AEs leading to withdrawal by Maximum Intensity
- Incidence of treatment emergent AEs leading to withdrawal by Maximum Relationship

Treatment emergent AE summaries will be ordered by alphabetical SOC and decreasing frequency of PT within SOC in the CZP column for tables including event counts.

A listing will be presented for SS for treatment emergent AE leading to withdrawal and follow the same display of output as described in [Section 5.4.1.2.2](#) . The other similar AE data handling rule will be also followed in [Section 5.5.1.2](#).

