A listing will be presented for SS for AEs including TEAE and non-TEAE. This listing will follow the same structure as described in [Section 5.4.1.2.2](#).

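### SAP Table 6-1 can list a negative duration for adverse events that ended before the first dose, and too small an upper bound for some resolved events in withdrawn participants

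*SAP*

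**What the plan says.** **Which rule governs.** SAP Section 6.1.6.2 first gives rules for partial dates and names AE duration among their purposes. It then sends the duration calculation to Table 6-1: "Missing or partially missing date and/or times will be imputed as described in" that table.

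**Missing start.** The row for a missing start day and time reads "Duration = <[(D2 - D0)*24 + (T2 - T0)]/24 d". The origin is fixed: "For a participant in the SS, D0 and T0 are the date and time of dosing". Only screen failures are counted from the screening visit, at 00:00. Nothing requires the end to fall after dosing.

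**Start-date rule in the same section.** A wholly unknown start is set to the date of dosing. If that gives "an imputed start date that is after the specified end date, then use January 01 of the year of the end date", or the screening date where that is later.

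**Missing end, resolved AE.** The row prints an upper bound of discharge day minus onset. Discharge is the end-of-study visit for completers and "the date of discontinuation for study participants that were withdrawn". Date of last contact replaces it only for AEs known to start after discontinuation. The row for both dates missing uses the same discharge day, with D0 in place of onset.

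**Where duration appears.** It is a column of the treatment-emergent SAE listing (SAP 5.4.1.2.2). Two other listings follow that structure: "A listing will be presented for SS for treatment emergent AE leading to withdrawal" (5.4.1.2.3) and "A listing will be presented for SS for AEs including TEAE and non-TEAE" (5.5.1.3).

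**Observation window.** Protocol Section 8.3.1 collects AEs from consent to the SFU visit. SAP Section 5.1.1.1.3 allows up to 28 days of Screening and places the SFU 70 days after the last dose.

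**The concern.** In (a), AEs are collected before dosing and non-treatment-emergent AEs are listed with their duration, so an AE that resolved in Screening falls within the missing-start row. Its end precedes the origin that the row imposes, and the result is below zero. The same section foresees an end before dosing and handles it, so two rules give different answers for one quantity.

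In (b), an upper bound is valid only if the AE had resolved by the date used. Discontinuation need not be that date: AE collection runs to the SFU, the table itself expects AEs that start after discontinuation, and SAP Section 5.2 lists premature termination and final contact as separate dates. An AE present at discontinuation that resolved later would be listed as shorter than it was. This can reach the treatment-emergent SAE and AE-leading-to-withdrawal listings, where a reader may look at how long an event lasted.

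**Working it through.** The plan states no duration to reproduce. The table's one numeric constant is right: 23:59 = 23 + 59/60 = 23.983 h, given as 23.98. All dates below are assumptions, counted from the first dose as Day 0.

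**(a) Start missing, AE ended before the first dose**

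Inputs: screening visit Day -20, first dose Day 0 at 09:00, AE end at 12:00 on the day shown.

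- Table 6-1: [(D2 - D0) × 24 + (T2 - T0)]/24 with D0 = 0 and T0 = 9.
- Counted from screening: the same formula with D0 = -20 and T0 = 0.

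| AE end | Table 6-1 | From screening visit |
|---|---|---|
| Day -14 | (-336 + 3)/24 = -13.875 d | (144 + 12)/24 = 6.5 d |
| Day -5 | (-120 + 3)/24 = -4.875 d | (360 + 12)/24 = 15.5 d |
| Day -1 | (-24 + 3)/24 = -0.875 d | (456 + 12)/24 = 19.5 d |

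The start-date rule gives the right-hand column if the screening date is later than January 01 of the end year and the start time is taken as 00:00. The second condition is an assumption, because for a wholly unknown start the rule gives a time only when the imputed date is the dosing date. When the AE ends after dosing the two rules agree: for Day 10 at 12:00, both give (240 + 3)/24 = 10.125 d.

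The fallback is not always a safe bound. Take screening on December 20, AE end on January 5 at 12:00 and first dose on January 10. January 01 is later than screening, so it becomes the start, and the listed bound is 4 + 0.5 = 4.5 d. An AE that began on the screening date would have lasted up to 16 + 0.5 = 16.5 d.

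**(b) Resolved AE, end date missing, participant withdrawn**

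Inputs: AE onset Day 50, last dose Day 56, discontinuation Day 60, last contact at the SFU on Day 56 + 70 = 126.

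- Table 6-1 bound: 60 - 50, printed as < 10 d.
- Bound using last contact: 126 - 50, that is < 76 d.
- If the AE was present at discontinuation and resolved later, the true duration lies between 10 and 76 d.
- An AE starting on Day 61 in the same participant is bounded at 126 - 61, that is < 65 d, because the last-contact exception applies to it.

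The bound can be too small by up to last contact minus discontinuation:

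- here, 126 - 60 = 66 d (59 to 73 d with the ±7-day SFU window);
- discontinuation on the day of the last dose: 70 d (63 to 77 d);
- discontinuation 14 days after the last dose: 70 - 14 = 56 d (49 to 63 d);
- discontinuation and last contact on the same day: 0 d.

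**The case against.** The case for leaving the text alone has four parts.

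1. **The two rule sets can be read together.** AE duration is a stated purpose of the start-date rules, so a programmer could impute the start first. But the section hands duration to Table 6-1, and its missing-start row supplies its own origin with no fallback. At best the order of the two rules is undefined.

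2. **The impact is small.** This stands. Duration is a listing column and no summary of it is specified. A reader might infer that negative values could appear in the treatment-emergent SAE or AE-leading-to-withdrawal listings. The documents do not support that: a treatment-emergent AE must start on or after the first administration (SAP 5.4.1.2.2), and an AE that ended before the first dose cannot have done so. The negative value belongs to the all-AE listing.

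3. **Later observation of withdrawn participants is not shown to be routine.** This also stands. The Protocol's Schedule of Activities has one combined column for SFU and early discontinuation, and a separate SFU after an Early Discontinuation Visit is spelled out only for pregnancy (Protocol 8.3.5). Nor do the documents say that an AE causing withdrawal is usually still present on that date. So (b) is conditional. The last-contact exception does show that the SAP expects contact after discontinuation in some cases.

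4. **The cases are rare.** Of 30 planned participants, (a) needs an AE with an unknown start and a known end before dosing. (b) needs a withdrawal and an end date that is wholly missing, since a known month or year is imputed. No frequency can be derived from the documents.

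**Conclusion.** Both rules are wrong as written, with low impact.

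(a) For a Safety Set participant whose AE has a missing start and ended before the first dose, Table 6-1 returns a negative duration; its size is the time from AE end to first dose. The example value of -4.875 d rests on assumed dates. This part conflicts with the section's own start-date rule.

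(b) For a resolved AE with no end date in a withdrawn participant, the printed upper bound is false if the AE began on or before discontinuation and resolved after it. In the example, < 10 d is printed where up to 76 d is possible, assuming last contact at a 70-day SFU. A reader might take this part, too, as a contradiction of the start-date rule. It is not: it concerns end dates, and conflicts with the AE collection window and with the table's own last-contact exception. Nor is discontinuation minus onset a lower bound in general; it is one only if the AE was still present at discontinuation.

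AE incidence and the PK endpoints are unaffected.

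**What to change.** Amend Table 6-1 in two places.

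1. **Missing-start row.** When the AE end precedes the first dose, set D0 to the screening visit date and T0 to 00:00, as the table already does for screen failures. Align the start-date rule for duration purposes, so that its January 01 step cannot shorten the bound when Screening spans the new year.
2. **Both missing-end rows.** For resolved AEs in withdrawn participants, define the discharge day as the later of date of discontinuation and date of last contact. Limit this to resolved AEs. For an ongoing AE, discontinuation is already a valid basis for the lower bound; moving it to last contact could overstate that bound unless ongoing status was confirmed then.

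The cost is a few lines of SAP text and a small change to the duration derivation. No new data are needed: visit dates, premature termination and final contact are already listed under SAP Section 5.2.

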**Table 6–1: Calculation rules for duration**

Data availability	Onset date/time	Outcome date/time	Calculation rules
Start and end date missing	--/--	--/--	
For ongoing AE: Duration = >Discharge day – D0 d OR
 
For resolved AE: Duration = <Discharge day – D0 d OR
 
For a participant in the SS, D0 and T0 are the date and time of dosing and for screen failures, D0 is the date of the screening visit and T0 = 00:00h.
 
Discharge refers to the date of the end of study visit or the date of discontinuation for study participants that were withdrawn.
 
For any AEs with known start date/time after the date of discontinuation, the date of last contact will be used as the discharge day.

SS=Safety Set; IMP=investigational medicinal product.

### 6.1.7 AEs of Special Interest (AESIs)

An AE of special interest is defined as following events:

- Hy’s Law (as described in [Section 5.5.1.5.2](#))
- Serious infections, including opportunistic infections.
- Malignancies, including lymphoma.
- Serious cardiovascular events - also called Major Adverse Cardiac Events (MACE)
- Congestive heart failure.
- Demyelinating-like disorders.
- Aplastic anemia, pancytopenia, thrombocytopenia, neutropenia, and leukopenia.
- Serious bleeding events.
- Lupus and lupus-like syndrome.
- Serious skin reactions (eg, Stevens-Johnson syndrome, toxic epidermal necrosis, and erythema multiforme).

Subsets on Adverse Events of Special Interest (AESIs) will either be extracted via Structured MedDRA Query (SMQ), via other automated queries based on search criteria specified by UCB or via manual medical review from the set of TEAEs or serious TEAEs.

Some types of AESIs are identified manually. For those, textual reporting in the CSR is deemed sufficient and no additional summary tables need to be generated. For others, especially those with automated search criteria additional TEAE summary tables are planned.

All manual searches and reviews have to be occurred prior to data cleaning meeting(DCM) and data evaluation meeting (DEM). A final review after database lock will be also executed in the framework of the data cleaning and data evaluation meeting.

The MedDRA SMQ terms are based on MedDRA version 23.1. In case that later MedDRA versions will be used, the appropriateness and spelling of the terms need to be reviewed and adapted accordingly.

The following summary tables will be produced for AESIs:

- TEAEs by SOC, HLT and PT for AESIs along with number and percentage summary
- Serious TEAEs by SOC, HLT and PT for AESI along with number and percentage summary

All AESIs the term(s) for extraction are specified in Table 6–1:

PUBLIC COPY  
This document cannot be used to support any marketing authorization application and any extensions or variations thereof.

**Table 6–1: Adverse Events of Special Interest (AESIs)**

AESIs term and other AE subsets	Extraction way	Term of SMQ (for SMQ extraction only) or other search strategy
AESIs: Infections, including serious opportunistic infections and tuberculosis	1) Serious infections	
	2) Opportunistic infections including tuberculosis, manual	2) UCB defined search criteria for opportunistic infections including Tuberculosis
AESIs: Malignancies, including lymphoma	1) SMQ 2) SMQ	1) SMQ="Malignant or unspecified tumours" 2) SMQ="Malignant tumours" Note: Non melanomic skin cancer will also be summarized by using HLT= "Skin neoplasms malignant and unspecified (excluding melanoma)"
AESIs: Congestive heart failure	1) Congestive heart failure, manual	
	2) Major adverse cardiovascular events (MACE)	2) UCB defined search criteria 
AESIs: Demyelinating-like disorders	SMQ	SMQ = "Demyelination (SMQ)"

AESIs term and other AE subsets	Extraction way	Term of SMQ (for SMQ extraction only) or other search strategy
AESIs: Aplastic anemia, pancytopenia, thrombocytopenia, neutropenia, and leucopenia	SMQ	SMQ="Haematopoietic cytopenias" on subset of serious TEAEs
AESIs: Serious bleeding events	SMQ	SMQ="Haemorrhages" on subset of serious TEAEs
AESIs: Lupus and lupus-like syndrome	Manual	Medical review of TEAE table
AESIs: Serious skin reactions (eg, Stevens-Johnson Syndrome, toxic epidermal necrosis, and erythema multiforme)	Manual	Medical review of serious TEAE table

- 1) Will include fatal and serious non-fatal myocardial infarctions, cerebrovascular events and congestive heart failures based on MedDRA terms and medical reviews.

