8.3.6 Adverse events of special interest

An AE of special interest is any AE that a regulatory authority has mandated be reported on an expedited basis, regardless of the seriousness, expectedness, or relatedness of the AE to the administration of a UCB product/compound. For CZP, the following events require immediate reporting (within 24 hours regardless of seriousness) to UCB:

- Hy's Law
 - Potential Hy's Law, defined as $\geq 3 \times \text{ULN}$ ALT or AST with coexisting $\geq 2 \times \text{ULN}$ total bilirubin in the absence of $\geq 2 \times \text{ULN}$ ALP, with no alternative explanation for the biochemical abnormality (ie, without waiting for any additional etiologic investigations to have been concluded). Follow-up information should be reported if an alternative etiology is identified during investigation and monitoring of the participant.
- Serious infections, including opportunistic infections.
- Malignancies, including lymphoma.
- Congestive heart failure.
- Demyelinating-like disorders.

- Aplastic anemia, pancytopenia, thrombocytopenia, neutropenia, and leukopenia.
- Serious bleeding events.
- Lupus and lupus-like syndrome.
- Serious skin reactions (eg, Stevens-Johnson syndrome, toxic epidermal necrosis, and erythema multiforme).

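### The AESI table in the SAP searches for cytopenias among serious TEAEs only, although the class is defined without a seriousness limit, so both planned AESI tables show the same events for it

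*SAP*

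**What the plan says.** Protocol 8.3.6 lists nine AESI classes and SAP 6.1.7 lists ten. Both give the blood-count class as "Aplastic anemia, pancytopenia, thrombocytopenia, neutropenia, and leukopenia", without the word *serious*. Both lists use that word where it is meant, for example "Serious infections, including opportunistic infections".

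SAP 6.1.7 says that AESI subsets are drawn "from the set of TEAEs or serious TEAEs" and refers to the AESI Table 6–1 for the extraction terms of every class. The label of the cytopenia row in that table does not say *serious* either, but its search rule is "SMQ='Haematopoietic cytopenias' on subset of serious TEAEs".

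On outputs, SAP 6.1.7 treats text in the study report as enough for some manually identified classes. It then adds: "For others, especially those with automated search criteria additional TEAE summary tables are planned". Two AESI tables are listed. The first is "TEAEs by SOC, HLT and PT for AESIs along with number and percentage summary"; the second has the same layout for serious TEAEs.

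**The concern.** The definition of the class and the rule that fills it disagree. A reader of the study report would take the cytopenia line in the AESI table of TEAEs as the count for the class defined in SAP 6.1.7 and Protocol 8.3.6. It would in fact be the count of serious cytopenias, repeated from the other AESI table.

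The class is one of those with an automated search, which are the classes SAP 6.1.7 singles out for summary tables. What is at stake is the AESI count for this one class.

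**Working it through.** No event rate, power or sample-size figure is involved, and the plan gives no figure to reproduce. The check compares definitions with search rules and then follows the rule through to the two tables.

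**Step 1. Definition against search rule (SAP 6.1.7 and the AESI Table 6–1)**

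| Class | Definition says *serious*? | Search in Table 6–1 | Limited to serious events? |
|---|---|---|---|
| Hy's Law | No | No row | – |
| Infections | Yes | (1) serious infections; (2) opportunistic infections including tuberculosis | (1) Yes; (2) No |
| Malignancies | No | Two SMQs | No (both) |
| Cardiovascular events (MACE) | Yes | Sponsor-defined criteria, in the heart failure row | Yes (footnote 1) |
| Congestive heart failure | No | Manual | No |
| Demyelination | No | SMQ | No |
| **Cytopenias** | **No** | **SMQ** | **Yes** |
| Bleeding | Yes | SMQ | Yes |
| Lupus | No | Manual review of TEAEs | No |
| Skin reactions | Yes | Manual review of serious TEAEs | Yes |

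Counts:
- SAP 6.1.7 has 10 classes: 4 say *serious* and 6 do not. Protocol 8.3.6 has 9 classes, of which 3 say *serious* (infections, bleeding, skin reactions).
- Table 6–1 has 8 rows and 2 + 2 + 2 + 1 + 1 + 1 + 1 + 1 = 11 searches. The additional skin-cancer term in the malignancy note is not counted.
- Five of the 11 searches are limited to serious events: serious infections, MACE ("Will include fatal and serious non-fatal myocardial infarctions" and similar events), cytopenias, bleeding and skin reactions. Four of the five belong to a class whose definition says *serious*. Cytopenias does not.
- Of the 6 classes without *serious*, 5 are searched in the table (Hy's Law has no row). Four have a search with no seriousness limit. Cytopenias is the only one whose sole search is restricted.

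**Step 2. What the two AESI tables will contain**

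Let C be the TEAEs that match the cytopenia SMQ and S the serious TEAEs.
- Extracted set under Table 6–1: C∩S.
- AESI table of TEAEs: C∩S.
- AESI table of serious TEAEs: (C∩S)∩S = C∩S.

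The two tables are therefore identical for this class, whatever terms the SMQ contains. With the SMQ run on all TEAEs, the first table would show C and the second C∩S. They would differ by exactly the non-serious cytopenia TEAEs.

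**Step 3. Size**

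The documents give no cytopenia rate, so the number omitted, k, is unknown. Planned enrolment is 30, and I assume a Safety Set of that size. If k participants have only non-serious cytopenia TEAEs, the class percentage is too low by k/30:
- k = 1: 1/30 = 3.3 points
- k = 2: 2/30 = 6.7 points
- k = 3: 3/30 = 10.0 points

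With a smaller set of 25, k = 1 gives 1/25 = 4.0 points. The 25 is only an illustrative lower value: in the plan it is the expected number completing Visit 13, whereas the Safety Set needs just one injection.

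Two features of the plan keep k small. Scheduled safety laboratory tests after dosing take place only at Week 12 and at SFU/EDV (Protocol 1.3). A laboratory abnormality becomes an AE only if the Investigator judges it clinically significant (Protocol Appendix 3).

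**The case against.** The strongest reply is that the SAP prespecifies the restriction. Section 6.1.7 allows either source set and sends the programmer to Table 6–1, which gives one unambiguous instruction. SAP Amendment 1 revised this table, changed the demyelination row and left the cytopenia row alone, which fits a deliberate choice. On that reading only the label is loose. The point about intent stands, and it is why relabelling is offered as an alternative below. But permission to use a serious-only source does not redefine a class, and the row's own label still lacks the word.

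A second reply is that the table does not follow the class labels strictly elsewhere. Opportunistic infections sit under a serious heading but are searched without a limit, and the defined-criteria search in the heart failure row (MACE) is serious-only. Both observations are correct. Heart failure, however, also has a manual search with no seriousness limit, so cytopenias remains the only class without *serious* that is restricted outright.

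A third is that identical tables are no defect in themselves, since bleeding shows the same result. That is true where the definition says *serious*. Here the identity shows that events meeting the definition are missing.

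A fourth is that little information is lost, and this largely stands. TEAEs are tabulated by preferred term without a threshold and all AEs are listed (SAP 5.5.1.3). Laboratory values outside the reference range are flagged and shift tables are planned (SAP 5.5.1.5). Protocol Appendix 3 gives blood dyscrasias as an example of events usually to be considered serious, which narrows the gap. Protocol 9.3 plans no AESI table. None of these outputs, however, gives the class count.

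The statement in Protocol 8.3.6 that AESIs are reported regardless of seriousness is a reporting rule, and this point does not depend on it.

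**Conclusion.** The concern holds and is minor. As written, the search rule gives a cytopenia AESI count that contradicts the definition of the class in both documents, and for this class the AESI table of TEAEs adds nothing to the AESI table of serious TEAEs.

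The shortfall is 3.3 percentage points per omitted participant, assuming 30 in the Safety Set. How many would be omitted cannot be derived from the documents and is probably few. The conclusion about the tables rests only on the wording of SAP 6.1.7 and its AESI table. No primary or secondary endpoint and no protocol-planned analysis is affected.

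**What to change.** In the cytopenia row of the AESI table, drop the restriction so that the SMQ runs on all TEAEs, and let the planned serious-TEAE AESI table show the serious subset. If a serious-only search is intended, add *serious* to the class in SAP 6.1.7 and in the row label, and state that this is narrower than Protocol 8.3.6.

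The AE listing also flags AESIs (SAP 5.4.1.2.2, applied to all AEs in SAP 5.5.1.3). The SAP does not say whether that flag follows the extraction table, so this should be settled at the same time. Two SAP tables carry the number 6–1 (duration rules and AESIs), so the correction should name the AESI table.

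The cost is one programming filter and a line of SAP text, with no new data. The downside is that AESI counts may be slightly higher and will include milder events.
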